## PROTOCOL SYNOPSIS

Title:	A multicentre, open-label study to evaluate the safety and diagnostic efficacy of mangoral in patients with known or suspected focal liver lesions and severe renal impairment.
Trial no.:	ASC-Man-P016
Trial name:	SPARKLE
EudraCT no.:	2019-001599-12
IND no.:	102,043
Clinical phase:	Phase III
Investigational medicinal product:	Manganese (II) chloride tetrahydrate ( $MnCl_2 \cdot 4H_2O$ ; working name: mangoral) powder for oral administration.
Study objective(s):	The overall objective of this study is to evaluate the safety and diagnostic efficacy of mangoral (equiv. to 800 mg $MnCl_2 \cdot 4H_2O$ ) in patients with known or suspected focal liver lesions and severe renal impairment.

### *Primary objective:*

- To assess the diagnostic efficacy of mangoral in liver MRI in terms of visualisation of detected focal liver lesions in combined MRI (CMRI: combined mangoral-enhanced and unenhanced MRI) compared to unenhanced MRI  
Lesion visualisation will be determined by qualitative assessments of lesion border delineation and lesion contrast compared to background liver on 4-point scales for up to 15 lesions per patient

### *Secondary objectives:*

- To assess the diagnostic efficacy of mangoral in liver MRI in terms of:
  - number of lesions detected by each MRI method (unenhanced MRI, mangoral-enhanced MRI, and CMRI)
  - visualisation of detected focal liver lesions in mangoral-enhanced MRI compared to unenhanced MRI (determination of visualisation will be done in the same way as for the primary efficacy variable)
  - confidence in lesion detection and localisation separately in unenhanced MRI, mangoral-enhanced MRI, and CMRI
  - lesion dimensions (independent off-site readers' assessment): longest diameter of the largest and smallest lesion
  - quantitative assessments by measuring percent signal intensity enhancement of liver, liver-to-lesion

contrast, signal-to-noise ratio, and contrast-to-noise ratio of up to 5 lesions per patient

- number of patients who had at least one new lesion identified on CMRI compared to unenhanced MRI alone
- To assess a proportion of patients having at least one malignant lesion identified on post-mangoral images that was not identified on pre-mangoral images.
- To evaluate the safety and tolerability of mangoral
- To evaluate the pharmacokinetics of manganese after a single dose of mangoral in a subgroup of patients (including a small number of dialysis patients)
- To evaluate the impact of diagnostic performance of CMRI and mangoral-enhanced MRI versus unenhanced MRI on the patients' management

**Design:** Multicentre, open-label, pivotal Phase III study to evaluate the safety and diagnostic efficacy of mangoral.

**Treatment:** Single oral dose of mangoral (800 mg manganese chloride [II] tetrahydrate, 500 mg L-alanine, and 800 IU vitamin D3).

**Population:** Adult male and female patients with severe renal impairment (Chronic Kidney Disease [CKD] or Acute Kidney Injury [AKI]) and who are being evaluated for known or suspected focal liver lesions. Approximately 80% of enrolled patients should have liver metastasis or other common focal liver lesions. The proportion enrolled HCC patients will be monitored jointly by the CRO/sponsor in order to achieve approximately 20% HCC patients in the overall study population. The CRO/sponsor may instruct individual sites, from time to time, to specifically and exclusively enrol patients with either non-HCC or HCC.

**PK subgroup:** Pharmacokinetic (PK) evaluations will be performed in a subgroup of patients included in the study. This PK subgroup will consist of 12 patients, including 4 patients currently on maintenance haemodialysis. These patients will be selected from few sites that are able to include these patients and follow PK requirements.

*Inclusion criteria:*

1. Patients who have been fully informed and have personally signed and dated the informed consent
2. Male and female patients 18 years and older
3. Patients who have known or suspected focal liver lesions based on medical history and previous laboratory and/or imaging examinations
4. Patients with severe renal impairment:
  - a. Chronic kidney disease (CKD) (estimated glomerular filtration rate [eGFR]

< 30 mL/min/1.73 m^2) based on medical history and previous laboratory examinations, at least once within the last 3 months prior to the Baseline Visit

OR

b. Acute kidney injury (AKI) with an increase in serum creatinine ≥ 0.3 mg/dL within 48 hours or ≥ 50% within 7 days, prior to the Baseline Visit

5. Female patients who are not of childbearing potential, or female patients who are of childbearing potential but are using highly effective contraception (including hormonal contraceptives, such as combined oral contraceptives, patch, vaginal ring, injectables, and implants, intrauterine device, intrauterine hormone-releasing system, vasectomised partner, and tubal ligation) or practising sexual abstinence (only accepted if this is the usual and preferred lifestyle of the patient), and have a negative urine or serum pregnancy test within 24 hours prior to the administration of contrast agent
6. Sexually active male patients (who are not vasectomised) must be willing to use condoms after administration of mangoral until the last follow-up visit
7. Patients who agree to comply with all study procedures as outlined within the study protocol and informed consent
8. Not applicable

*Exclusion criteria:*

1. Patients with simple liver cysts only
2. Patients who have received any investigational drug or were treated with an investigational device within 6 weeks prior to the Baseline Visit
3. Patients who have received any MRI contrast media within 6 weeks prior to the Baseline Visit or are scheduled to receive any other contrast medium other than mangoral before the last study visit
4. Patients who have previously been enrolled in the study and underwent mangoral-enhanced MRI
5. Patients who are clinically unstable or have an acute illness, as judged by the investigator; i.e. the underlying clinical condition is such that clinically relevant changes in condition can be reasonably anticipated during the study period
6. Patients with severe hepatic impairment (according to Child-Pugh score C)
7. Not applicable
8. Patients scheduled for surgery before the last study visit
9. Pregnant or lactating women
10. Patients with a history of severe allergies (e.g. anaphylaxis), as judged by the investigator

11. Patients with a known hypersensitivity to the IMP or any excipients in the IMP
12. Patients who are, in the investigator's opinion, unable to comply with the study requirements including follow-up procedures
13. Patients with known portosystemic shunts
14. Patients with encephalopathy, as judged by the investigator
15. Patients with neurodegenerative disorders
16. Patients with acute neurological disorders, as judged by the investigator
17. Patients with haemochromatosis
18. Patients receiving blood transfusion within 14 days prior to the Baseline Visit
19. Patients who cannot fast for 8 hours
20. Patients who cannot undergo MRI due to MRI incompatible pacemaker, metal implants, or other MRI contraindications
21. Patients with known inherited disorders of manganese metabolism
22. Patients with known pheochromocytoma
23. Patients with history of surgical/other interventional procedures or conditions which may interfere with absorption or excretion of IMP (e.g. small bowel obstruction, gastric bypass, gastric resection, biliary obstruction), as judged by the investigator
24. Patients who have been institutionalised by official or court order and therefore are not completely free in their decision-making process
25. Patients dependent on the sponsor, investigators, personnel of the trial site or any other individual, whose willingness to volunteer may be unduly influenced by the expectation, whether justified or not, of benefits associated with participation.

**Methodology:**

The study consists of the following periods/visits:

- Screening period (day -28 to -1; assessments can be performed anytime during the 4-week period): informed consent, inclusion/exclusion criteria, patient characteristics, serum pregnancy test (female patients of childbearing potential)
- Baseline period (day -1 to day 0, i.e. within 24 hours prior to the administration of mangoral): safety assessments, neurological assessments, unenhanced MRI examination of the liver (baseline MRI), pre-dose blood samples for manganese measurements, pregnancy test (female patients of childbearing potential)

- Day of MRI (day 0): intake of mangoral after a fast of at least 4 hours and after unenhanced MRI (note: fasting must be continued until after the mangoral-enhanced liver MRI examination has been performed (ie 4 [ $\pm$  1] hours after mangoral administration)
- Follow-up visits following contrast administration (24 [ $\pm$  4] hours, 48 [ $\pm$  4] hours, and 5 [ $\pm$  2] days post-dose): safety assessments, neurological assessment, blood samples for manganese concentrations.

*Note: In case a patient is not able to return for the follow-up visits to the study site, these follow-up assessments may be performed at an off-site location (e.g. at the patient's home or at an associated off-site clinic by a trained examiner): Patients with long travelling distances may stay at a hotel near the study site at the expense of the sponsor. If further adjustments are required, Visit 4 (at 24 [ $\pm$  4] hours) and Visit 5 (48 [ $\pm$  4] hours) can be performed as a remote visits, at the discretion of the investigator.*

- A subgroup of patients who underwent brain MRI due to any clinical reason within the last 6 months prior to mangoral-enhanced MRI may also undergo an optional brain MRI 7 (+ 2) days after mangoral-enhanced MRI of the liver

PK subgroup: additional blood samples (6 mL per time point) will be drawn for the determination of PK parameters on the day of the liver MRI examination (day 0) at 0.25, 0.5, 1, 2, 3, 4, 6, 8, and 12 hours post-dose.

Primary diagnostic efficacy in terms of visualisation of detected lesions will be evaluated centrally at an imaging core laboratory by three independent readers who are experienced in liver imaging. A fourth reader who is not involved in efficacy reads will track and match the detected lesions on unenhanced, mangoral-enhanced and CMRI to confirm lesion numbering and lesion location across the modalities. Lesion tracking will also confirm lesions that are identified on pre-mangoral, post-mangoral and CMRI images. Study MRIs will also be evaluated by the on-site radiologists for the assessment of secondary objectives and for clinical purposes. Both on-site and independent radiologists will be trained prospectively in a standardised way.

Efficacy variables:

*Primary efficacy variable:*

The primary efficacy endpoint will be the visualisation of detected focal liver lesions in combined MRI (CMRI, mangoral-enhanced MRI plus unenhanced MRI) as compared to unenhanced MRI.

Visualisation will be measured by two co-primary variables:

- lesion border delineation

- lesion contrast compared to liver background

Both parameters will be determined for each lesion (up to 15 lesions per patient) and by each of the three independent readers by qualitative assessment on 4-point scales with categories 'poor' (1), 'partial/moderate' (2), 'good' (3), and 'excellent' (4) lesion border delineation/lesion contrast.

Based on the scores on the 4-point scales, two sum scores will be calculated for each patient and separately for each MRI method: a lesion border delineation sum score and a lesion contrast sum score. Only lesions detected at baseline (unenhanced MRI) will be included in the assessment of diagnostic efficacy.

*Secondary efficacy variables:*

[figure not shown]
- Number of lesions detected by each MRI method: unenhanced MRI, mangoral-enhanced MRI, and CMRI (on-site and independent off-site readers' assessments)
- Visualisation of focal liver lesions in mangoral-enhanced MRI as compared to unenhanced MRI (independent off-site readers' assessment; visualisation will be assessed as for the primary efficacy endpoint)
- Confidence in lesion detection separately in unenhanced MRI, mangoral-enhanced MRI, and CMRI (3-point scale, on-site and independent off-site readers' assessments of up to 15 lesions per patient)
- Confidence in lesion localisation separately in unenhanced MRI, mangoral-enhanced MRI, and CMRI (3-point scale, on-site and independent off-site readers' assessments of up to 15 lesions per patient)
- Lesion dimensions (independent off-site readers' assessment): longest diameter of the largest and the smallest lesion
- Quantitative assessments will be performed for up to 5 detected lesions (independent off-site readers' assessment). These lesions will be the same for pre- and post-contrast assessments:
  - liver signal intensity (SI) enhancement (%)
  - liver-to-lesion contrast (LLC)
  - signal-to-noise ratio (SNR)
  - contrast-to-noise ratio (CNR)
- Change(s) in patients' management based on the diagnostic performance of CMRI or mangoral-enhanced MRI versus unenhanced MRI:
  - Any changes in patient management based on MRI findings (yes/no)
  - Next steps in patient management based on MRI findings (i.e. chemotherapy, surgery, local ablation procedure, combination therapy, or other [specify])

Subgroup analyses:

The primary efficacy endpoint will be evaluated in appropriate subgroups which will be defined in the statistical analysis plan (e.g. subgroups by MRI scanner's magnetic field strength, lesion type, lesion diameter, age, and eGFR).

Safety variables:	Vital signs, physical examination, neurological assessment, electrocardiogram (ECG), clinical safety laboratory testing (haematology, biochemistry, urinalysis), blood manganese concentrations, monitoring of adverse events, and evaluation of brain MRI in a subgroup of patients.
Pharmacokinetic variables	The following PK variables will be determined: AUC (area under the curve) for the interval 0-120 hours, $C_{\max}$ (maximum or peak concentration), $t_{\max}$ (time to achieve maximum concentration), $t_{1/2}$ (terminal half-life) and $Cl_{app}$ (total apparent clearance).
Statistical methods:	
The two co-primary variables (patients' lesion border delineation and patients' lesion contrast) will be analysed for the full analysis population (i.e. all patients who received mangoral and for whom all unenhanced/enhanced MRI are assessable). The superiority of CMRI over unenhanced MRI regarding both co-primary variables (using the mean score differences between the paired sum scores weighted by the number of lesions determined per patient) will be evaluated for each independent reader.
 
The study will be considered successful if the reading results of at least two of three independent readers demonstrate the superiority of CMRI versus unenhanced MRI for both lesion border delineation and lesion contrast. Hypotheses will be tested using a one-sided paired t-test.
 
A comparison of unenhanced MRI and mangoral-enhanced MRI alone will be evaluated in the same way as the primary analysis. The secondary efficacy variables will be analysed in an exploratory manner using descriptive statistics (including confidence intervals). Safety and PK data will be analysed descriptively.

Number of patients:	
Approximately 197 patients will be enrolled to ensure a sample size of 167 patients for the primary analysis at an overall study power of 80%, assuming 85% of the image sets being completely evaluable.
 
To adjust for testing the simultaneous success of two co-primary variables, the power of each individual test will be set to 90%. The simultaneousness does not influence the type I error. Thus, the tests will be performed at a global 1-sided level of significance of 0.025.

Number of sites:	Approximately 60 sites.

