Follow-up evaluations (FU 1, FU 2, FU 3) will be performed on 3 visits following contrast administration, at 24 ( $\pm$  4) hours, 48 ( $\pm$  4) hours, and 5 ( $\pm$  2) days post-dose, for safety assessments including clinical safety laboratory tests, measurement of blood manganese, ECG, vital signs, physical examination, including neurological assessments. Changes in concomitant therapies will be recorded. Follow-up evaluations at 24 ( $\pm$  4) hours and 48 ( $\pm$  4) hours can at the discretion of the investigator be performed as remote visits when required to ease the burden for the patient. Participants in the PK subgroup are required to have all assessments including blood samples as scheduled.

An additional follow-up visit (FU 4) for the optional brain MRI may be performed 7 (+ 2) days after mangoral-enhanced MRI of the liver only in those patients who underwent brain MRI due to any clinical reason within the last 6 months prior to mangoral-enhanced MRI and for whom previous brain MRI images are available for comparison (Section 6.2.4.1.2).

In a subgroup of patients, additional blood samples (6 mL per time point) will be drawn for the determination of pharmacokinetic parameters on the day of the liver MRI examination (day 0) at 0.25, 0.5, 1, 2, 3, 4, 6, 8, and 12 hours post-dose (Section 6.4). This PK subgroup will consist of 12 patients, including 4 patients currently on maintenance haemodialysis.

Each unenhanced and each mangoral-enhanced liver MRI examination will consist of axial T1- and T2-weighted image sequences and a diffusion-weighted imaging (DWI) sequence. Details of MRI acquisition parameters are described in Section [6.2.4.1.1](#).

Primary diagnostic efficacy in terms of visualisation of detected focal liver lesions will be evaluated centrally at an imaging core laboratory by 3 independent readers (Section [6.2.5](#)). Reading will be performed in 3 parts (Part I: unenhanced MRI alone; Part II: combined MRI, i.e. paired reading of both unenhanced and mangoral-enhanced images; Part III: mangoral-enhanced MRI alone). There will be a minimum 2-weeks gap between the reads to reduce recall bias. All independent central readers will be blinded to clinical data, site, and country information.

The site investigators will also evaluate unenhanced and mangoral-enhanced MRI images (on-site read). Their assessments will be used for the analysis of secondary variables.

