## 8 STATISTICS

### 8.1 Statistical and analytical plans

All statistical analyses will be outlined in detail in a statistical analysis plan which will be prepared and signed prior to any study-specific analyses. In general, all continuous measures will be summarised descriptively, including the number of available values, minimum, 1st quartile, median, mean, standard deviation, 3rd quartile, maximum, if appropriate. Categorical data will be presented by frequency and percentage. Ordinal ratings may be handled as continuous data, if appropriate.

Inferential methods will be based on a significance level of 0.05 for two-sided tests and 0.025 for one-sided tests. All statistical significance tests besides the primary efficacy analysis should be interpreted in an exploratory manner.

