### **8.1.14 Determination of sample size**

The primary endpoint analysis consists of two co-primary one-sided t-tests at the conventional one-sided significance level of 0.025. Following the FDA's draft guidance on multiple endpoints in clinical trials, adjustment of the type-I-error is not necessary since both primary variables

need to show superiority simultaneously. Nonetheless, this affects the type II error. To counteract the inflation of the type II error, each test's power is set to 0.9 to achieve a study power of at least  $0.9 \times 0.9 = 0.81$ .

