#### Effect size

The primary efficacy is based on qualitative parameters, but no exact estimates are available from previous studies due to the use of DWI in this study. A study investigating a manganese-based contrast agent with T1 / T2 and DWI comparing also unenhanced versus CMRI [39] reported qualitative score results on a scale from 1 to 5. These results are used to derive estimates for mean and standard deviation (SD) and scaled down for the 1 to 4 scale used in this study. Calculating an average score per patient and averaging readers after rescaling, leads to averages of 2.3 for unenhanced versus 2.6 for CMRI. This is a difference of 0.3 with each sample's standard deviation of ~1.9, or ~1.5 after rescaling. For estimation of the SD of the samples' differences, a high correlation (0.8) is assumed, which results in 0.95.

[figure not shown]
Conservatively assuming no effect of the subpopulation of the HCC patients (20% of the study population), the effect is  $0.3 \times (1-0.2) = 0.24$ .

Sample size calculation was performed using SAS® version 9.4 resulting in 167 patients needed for analysis (Table 11, Figure 2). Assuming, that only 85% of the image sets will be completely evaluable (all enhanced and unenhanced liver MRI images) and that no patients will drop out (since the efficacy procedure is completed within a few hours for each patient), 197 patients need to be included in the study.

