10.2 Inferential Statistics

Inferential methods will be based on a significance level of 0.05 for 2-sided tests and 0.025 for 1-sided tests. All statistical tests besides the primary efficacy analysis will be interpreted in an exploratory manner.

The testing of efficacy will be done separately for each of the 3 independent readers and will be based on mean scores of BD and LC. For each independent reader, the hypotheses for the superiority of CMRI versus unenhanced MRI will be tested using a 1-sided paired t-test comparing mean score differences between treatment groups, assuming that the differences are normally distributed. As a sensitivity analysis, the non-parametric Wilcoxon signed-rank test will be also performed.

In all statistical tables, p-values will be reported as specified by the statistical program used, at least up to three decimal places. The p-values less than 0.001 will be reported as provided by SAS (e.g. '<0.001').

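### The primary test compares two full MRI examinations with one; testing the planned enhanced-alone versus unenhanced comparison as a gated key secondary would let the trial attribute a gain to the contrast

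*Protocol*

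**What the plan says.** - **Reads.** Protocol 3 and 6.2.5.1 and SAP 9.1 define three central reads: Part I (unenhanced), Part II (both examinations read together, CMRI) and Part III (mangoral-enhanced alone). Protocol 3 adds: "Each unenhanced and each mangoral-enhanced liver MRI examination will consist of axial T1- and T2-weighted image sequences and a diffusion-weighted imaging (DWI) sequence". Part II therefore offers two complete sets, and Parts I and III one each.
- **Primary test.** Protocol 2.1.1 and SAP 8.1 state the primary objective as CMRI compared with unenhanced MRI. Protocol 8.1.3 and SAP 13.7.1 test, for each reader, whether the mean Part II minus Part I difference per lesion exceeds zero. A reader succeeds if both border delineation (BD) and lesion contrast (LC) are significant, and the trial succeeds if two of three readers do.
- **Part III versus Part I.** The synopsis (Statistical methods) says: "A comparison of unenhanced MRI and mangoral-enhanced MRI alone will be evaluated in the same way as the primary analysis". Protocol 8.1.4 and SAP 13.7.2 repeat this. The comparison is outside the success rule. Protocol 8.1 says "All statistical significance tests besides the primary efficacy analysis should be interpreted in an exploratory manner", and SAP 10.2 says "All statistical tests besides the primary efficacy analysis will be interpreted in an exploratory manner".
- **Scoring rule for the combined read.** Neither document says how one score per lesion is taken from the paired images. Reading details are left to the imaging manual and the independent review charter (Protocol 3, 6.2.3.1 and 6.2.4.2).

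**The concern.** A second examination brings a new breath-hold, a new slice position and new noise, whatever the agent does. If a lesion's Part II score follows whichever set shows it better, the expected Part II minus Part I difference is above zero even for an inert agent. Protocol 1.1.3 describes manganese agents as raising T1-weighted signal, so the repeated T2 and DWI sequences may act partly as an extra look.

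The planned safeguards have other targets. The two-week gap addresses recall, and the blinding addresses clinical information. No control read of two unenhanced sets is planned.

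What is at stake is interpretation. The trial can confirm that adding the examination helps. As planned, it has no confirmatory statement that the contrast is the reason.

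**Working it through.** **1. The plan's own figures.** Protocol 8.1.14 uses "two co-primary one-sided t-tests at the conventional one-sided significance level of 0.025", and "each test's power is set to 0.9 to achieve a study power of at least" 0.9 × 0.9 = 0.81. On the effect: "This is a difference of 0.3 with each sample's standard deviation of ~1.9, or ~1.5 after rescaling". The assumed correlation is 0.8, and the effect after allowing for HCC patients is 0.3 × (1 − 0.2) = 0.24.

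- SD of differences = √(2 × 1.5² × (1 − 0.8)) = √0.9 = 0.949 (protocol: 0.95).
- The one-sided paired t-test (noncentral t) gives n = 167 with power 0.902, and 167 / 0.85 = 196.5, so 197. All 15 rows of Table 11 reproduce.
- SAP 9.3 gives 59 evaluable patients for an effect size of 0.42. Read as a standardised effect at 90% power per test, this needs 60 (normal approximation) or 62 (noncentral t). Two of three independent readers at 0.81 each gives 3 × 0.81² × 0.19 + 0.81³ = 0.905, which matches the stated 90%.

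The sample-size arithmetic is not the issue here.

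**2. Rejection per test with no contrast effect.** Let b be the mean second-look gain in score points. The documents give no value, so b is an assumption. With no contrast effect the mean difference equals b, and the noncentrality is b / (0.949/√n). The standard error is 0.949/√59 = 0.1235 or 0.949/√167 = 0.0734. SAP 9.3 states no SD for its revised calculation, so the n = 59 column borrows the protocol's; a smaller SD would raise these figures.

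| Assumed b (points) | n = 59 | n = 167 |
|---|---|---|
| 0 | 2.5% | 2.5% |
| 0.02 | 3.6% | 4.6% |
| 0.05 | 5.9% | 10.0% |
| 0.10 | 12.2% | 27.2% |
| 0.15 | 22.2% | 52.8% |

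**3. Effect of the success rule.** Suppose readers err independently and BD and LC are fully correlated. With p the per-test figure, trial-level rejection is 3p²(1 − p) + p³.

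| Assumed b (points) | n = 59 | n = 167 |
|---|---|---|
| 0 | 0.2% | 0.2% |
| 0.05 | 1.0% | 2.8% |
| 0.10 | 4.1% | 18.2% |

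The rule lowers the error, but all readers see the same extra images, so it does not remove a shift they share. If the three readers always agreed, the trial-level figure would equal the per-test figure.

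**4. Range of b.** If readers score from one set, or average the two, b = 0. At the other extreme, suppose each patient's score always came from the better of two equivalent examinations whose difference is normal with SD 0.949. Then b = 0.949/√(2π) = 0.38. Nothing in the documents places b within this range.

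**5. Part III versus Part I.** This sets one examination against one, so b does not enter.

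**The case against.** The strongest reply is that the primary objective is explicitly CMRI versus unenhanced MRI, and that a null of zero mean difference is the right null for that question. This stands in full. The point limits what can be attributed to the contrast and finds no fault in the primary test.

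Other replies also have weight:

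- **The mechanism depends on a reading rule that is not in these documents.** This stands, and the size is therefore unknown.
- **Lesion selection may pull the other way.** The primary analysis uses only lesions already seen on unenhanced MRI (Protocol 6.2.2.1, SAP 9.2.2), and regression to the mean could lower their later scores. This makes the net shift uncertain without excluding it.
- **Other measures compare single examinations.** Liver signal enhancement, liver-to-lesion contrast, SNR and CNR do so (Protocol 6.2.3.5, SAP 11.2.5), as do lesion counts and confidence by method. This is true, but they are descriptive and are not the BD and LC scores.
- **Part III versus Part I is already well reported.** It gets the same tests, subgroup analyses and a forest plot (SAP 13.7.2 and 13.7.3). Only its formal status is missing. Protocol 8.1.4 names it apart from the other secondary variables, which might suggest a special standing, but Protocol 8.1 and SAP 10.2 settle it as exploratory.
- **Part III is read without the unenhanced set.** Contrast could help in the combined read and still fail to show here. This stands and is reflected in the claim wording proposed below.

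**Conclusion.** This is a worthwhile, low-cost improvement. The primary test answers its stated question, but it compares two sets with one, and the only one-against-one comparison of reader-scored BD and LC is exploratory. Under no contrast effect, an assumed second-look gain of 0.05 to 0.10 points raises rejection per test from 2.5% to about 6–12% (n = 59) or 10–27% (n = 167). These figures rest on the protocol's SD of differences of 0.949 and apply before the success rule. With no such gain, the level stays at 2.5%.

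A reader might infer that the primary test is invalid, or that an inert agent would usually pass it. The documents do not support that. Very high rejection rates need readers to take the better set for nearly every lesion, which neither document says, and they describe one test in one reader rather than trial success. The inflation is possible but unquantified.

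**What to change.** Leave the primary analysis unchanged. In Protocol 8.1 and 8.1.4 and SAP 10.2 and 13.7.2, make Part III versus Part I a key secondary in fixed sequence: if and only if the primary succeeds, test BD and LC for each reader at one-sided 0.025, with the same two-of-three rule. Specify this before database lock, while the central reads are masked to the sponsor and the trial statisticians (SAP 9.4).

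State the claims in advance:

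- Primary success supports saying that adding a mangoral-enhanced examination improves visualisation.
- Success at the second step supports attributing the gain to the contrast.
- Failure at the second step leaves attribution unconfirmed, not disproved.

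The fixed sequence costs no alpha, and no new data or reads are needed. The cost is a protocol and SAP amendment: Protocol 8.1.11 requires a protocol amendment where the confirmatory analysis is affected, and Protocol 10.2 reserves amendments for exceptional cases. The second step may also fail because Part III is read without the unenhanced set, and its power has not been calculated.
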